# 16.8 Intellectual Property Rights

All Intellectual Property Rights owned by or licensed to either GW or the PIs, other than those arising from the clinical study, will remain their property. All Intellectual Property Rights arising out of the clinical study will vest in or be exclusively licensed to GW and, as such, the PI should promptly disclose all knowledge to GW and refrain from using such knowledge without the prior written consent of GW.

# 16.9 Confidential Information

GW and the PI should ensure that only personnel directly concerned with the study should be party to confidential information and that any information coming to either party about the other during the course of the study should be kept strictly confidential and should not be disclosed to any third party or made use of without the prior written consent of the other.

# APPENDIX 1 SCHEDULE OF ASSESSMENTS

#### **Blinded Phase**

Visit Number	1	2	3	4	5	6	7	8	9	10	11	12 (Tel.)	Safety Calls*
Day	-35	-28	1	15	29	43	57	71	85	113	123	151	
Visit Window		±7	+3	±3	±3	±3	±3	±3	±3	±3	+3	+3	
Informed consent/assent	Х												
Eligibility Criteria	Х	Х	Х										
Randomization			Х										
Demographics	Х												
Medical history	Х												
Vital signs and BP	Х		Х	Х	Х	Х	Х		Х	Х	Х		
Postural BP	Х		Х		Х								
Physical examination (including height and body weight)	Х		Х	Х	Х	Х	Х		Х	Х	Х		
ECG	Х		X§	Х	Х	Х	Х		Х	Х	Х		
Clinical laboratory blood sampling	Х		Х	Х	Х	Х	Х		Х	Х	Х		
Clinical laboratory IGF-1 testing			Х							Х			
Clinical laboratory urine sampling (dipstick urinalysis)	Х		Х	Х	Х	Х	Х		Х	Х	Х		
Urine/serum THC screen	Х												
Pregnancy tests (if appropriate)	Х		Х		Х		Х		Х	Х			

Visit Number	1	2	3	4	5	6	7	8	9	10	11	12 (Tel.)	Safety Calls*
Day	-35	-28	1	15	29	43	57	71	85	113	123	151	
Visit Window		±7	+3	±3	±3	±3	±3	±3	±3	±3	+3	+3	
Pharmacokinetic blood sampling			Х							Х			
AED concentration			Х		Х		Х		Х	Х			
TSC1 and TSC2 mutation status (if unknown and consent is given)	Х												
AEs	Х	Х	Х	Х	Х	Х	Х	Х	Х	Х	Х	Х	Х
Concomitant medications	Х	Х	Х	Х	Х	Х	Х	Х	Х	Х	Х	Х	Х
Inpatient epilepsy-related hospitalizations		Х	Х	X	Х	х	X	Х	Х	х	х	Х	Х
Suicidality/C-SSRS/Children's C-SSRS	Х		Х	Х	Х	Х	X		Х	Х	Х		
Vineland-II			Х							Х			
SGIC/CGIC			Х							Х			
PGIC			Х							Х			
SGIC-SD/CGIC-SD			Х							Х			
QOLCE/QOLIE-31-P			Х							Х			
Wechsler Tests			Х							Х			
CBCL/ABCL			Х							Х			
SCQ			Х							Х			
Tanner Staging (where appropriate)			Х							Х			
Menstruation question (where appropriate)			Х							Х			

Visit Number	1	2	3	4	5	6	7	8	9	10	11	12 (Tel.)	Safety Calls*
Day	-35	-28	1	15	29	43	57	71	85	113	123	151	
Visit Window		±7	+3	±3	±3	±3	±3	±3	±3	±3	+3	+3	
Patient IVRS and paper diary review (seizures, AE information, concomitant AEDs, rescue medication, IMP dosing)			Х	Х	X	Х	x		Х	Х	Х		
IVRS and diary training		Х											
IMP dispensing			Х	Х	Х	Х	Х		Х	Х			
Collection of IMP				Х	Х	Х	Х		Х	Х	Х		
IMP compliance review				Х	Х	Х	Х		Х	Х	Х		
Study Medication Use and Behavior Survey										Х	ţ†		

\*Telephone safety calls will be completed every two days during titration, one week after the end of titration and, for patients not entering the OLE, weekly from Visit 10 to Visit 12. If the call falls on a weekend, it is permitted to schedule the call for the Friday before or Monday after the weekend instead.

ECG must be re-assessed four hours (±30 minutes) post-dose.

•Only for patients weighing > 20 kg.

†Performed at final dosing visit (End of Treatment/Withdrawal visit or End of Taper visit, as applicable) for patients 12 years of age and older only.

\*Telephone safety calls will be completed every two days during the blinded transition, titration and one week after the end of titration. If the call falls on a weekend, it is permitted to schedule the call for the Friday before or Monday after the weekend instead.

[figure not shown]
†Performed at final dosing visit (End of Treatment/Withdrawal visit or End of Taper visit, as applicable) for patients 12 years of age and older only.

# APPENDIX 2 TANNER STAGING

(Reproduced with permission from the New England Journal of Medicine).

The following is to be completed for all female adolescent patients (i.e., 10 to less than 18 years of age at the time of signing the informed consent/assent form, or earlier if clinically indicated by onset of menarche or other signs of precocious puberty).

# Female Development & Pubic Hair

Please check the box next to the most appropriate stage; in the event that qualifying characteristics are not within the same stage, defer to the lesser stage as the overall Tanner Score.

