#### Growth and Development (in patients less than 18 years old):

- Change in serum insulin-like growth factor-1 (IGF-1) levels.
- Change in Tanner Staging score (for patients aged 10–17 [inclusive]).

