#### 9.2.14 Tanner Staging

The pubic hair growth (both sexes), genital (males only) and breast (females only) development of all adolescent patients (i.e., 10 to 17 years of age at the time of signing the informed consent form, or earlier if clinically indicated by onset of menarche or other signs of precocious puberty) will be assessed using Tanner Staging (see APPENDIX 2). The patients will undergo a discreet physical examination and be assigned a value under each category of Pubic Hair Growth (both sexes), Genitals (male patients only), and Breasts (female patients only).

Once a patient reaches a score of V (i.e., 5) the examination need not be performed again.

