#### **Blinded Phase:**

The number of patient responders (including the key secondary endpoint) and the number of patients seizure-free will be summarized and analyzed using a Cochran–Mantel–Haenszel test stratified by age group. In addition, the difference in proportions and the odds ratio, together with 95% CIs, comparing the treatment groups will be presented.

For number of seizure-free days, use of rescue medication, number of episodes of *status epilepticus* (only if there is a sufficient number of patients with data), Vineland-II, Wechsler scales, CBCL, ABCL, SCQ, QOLCE and QOLIE-31-P scores, the data will be summarized at baseline and over the treatment period, and at each time-point (or 28-day period, as appropriate) during the maintenance period. Changes from baseline to the average over the treatment period (or at end of study) will be analyzed using ANCOVA (or appropriate non-parametric methods if data are found to be not normally distributed). The models will include baseline and age group as covariates and treatment group as fixed factor. The treatment difference, together with the 95% CIs will be presented.

The changes in composite focal seizure score, change in total seizures, the number of seizures by subtype and the number of 'other' seizures will be analyzed using the same analysis as the primary endpoint.

SGIC-SD/CGIC-SD, SGIC/CGIC and PGIC assessments recorded at the end of treatment will be analyzed with ordinal logistic regression using the proportional odds model.

Changes from baseline for IGF-1 levels will be summarized by treatment group and plotted against the Tanner Stages, weight, and height.

Tanner Stages will be evaluated and summarized descriptively at each time-point in terms of frequency and proportions. Number (%) of patients with changes in Tanner Stages will be summarized by treatment group.

In order to explore the robustness of the primary analysis, further sensitivity analysis (in addition to that already detailed in Section 13.6.2.1) may be specified in the SAP.

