# Tanner Stage 1 (Prepubertal, typically 10 years and younger)

- No glandular tissue; areola follows the skin contours of the chest.
- No pubic hair at all.

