# Male Genital Development & Pubic Hair

Please check the box next to the most appropriate stage.

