5.6.4.6 Growth and Development

IGF-1 levels will be analyzed as part of the clinical laboratory testing. IGF-1 levels will be summarized on a continuous scale, including change from baseline, by treatment arm.

For the blinded phase only, change from baseline to the end of treatment visit for IGF-1 levels will also be plotted against the Tanner Stages, weight, and height recorded at baseline.

The pubic hair growth (both sexes), genital (males only) and breast (females only) development of all adolescent patients (i.e., 10 to less than 18 years of age at the time of signing the informed consent form, or earlier if clinically indicated by onset of menarche or other signs of precocious puberty) will be assessed using Tanner Staging. The patients will undergo a discreet physical examination and be assigned a value under each category of Pubic Hair Growth (both sexes), Genitals (male patients only), and Breasts (female patients only).

Tanner Stages will be summarized on a categorical scale, by treatment arm.

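### Appendix 2 records one overall Tanner stage, for girls the lesser of breast and pubic hair, although Protocol 9.2.14 and SAP 5.6.4.6 assign a value to each; a change in one characteristic can go unrecorded

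*Protocol*

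**What the plan says.** Protocol Section 9.2.14 cites Appendix 2 as the staging tool and says that patients will "be assigned a value under each category of Pubic Hair Growth (both sexes), Genitals (male patients only), and Breasts (female patients only". SAP Section 5.6.4.6 repeats this. On that text a girl has two values (breast, pubic hair) and a boy has two (genital, pubic hair).

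Appendix 2 is laid out differently. Each female stage pairs a breast description with a pubic hair description. Stage 1, for example, combines "No glandular tissue; areola follows the skin contours of the chest" with "No pubic hair at all". The assessor ticks one stage and, "in the event that qualifying characteristics are not within the same stage, defer to the lesser stage as the overall Tanner Score". The male sheet pairs genital and pubic hair descriptions in the same way. It says only "Please check the box next to the most appropriate stage", with no instruction for a patient whose two characteristics fall in different stages.

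The endpoint in Protocol Section 4.1.2 is worded as one score: "Change in Tanner Staging score (for patients aged 10–17 [inclusive". For its analysis, Protocol Section 13.6.3 says: "Number (%) of patients with changes in Tanner Stages will be summarized by treatment group". The corresponding SAP sentence is: "Tanner Stages will be summarized on a categorical scale, by treatment arm". It does not say which value is tabulated, and it does not mention change.

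**The concern.** A site that follows Appendix 2 to the letter produces one number per patient. A site that follows Section 9.2.14 produces two. The two cannot be recovered from their minimum.

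The minimum also behaves badly as a measure of change. It moves only when the lagging characteristic moves, so it can hide an advance but cannot create one. Change in Tanner stage is a named growth and development endpoint, and the protocol's analysis counts patients whose stage changed, which is the quantity this rule reduces. In the blinded phase, staging is scheduled only at Visit 3 (Day 1) and Visit 10 (Day 113), so no reading in between could show what the overall score missed.

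**Working it through.** The plan gives no figure to reproduce here. The check is to apply the Appendix 2 rule to every possible pair of stages.

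**Inputs.** Breast stage B and pubic hair stage P each run from 1 to 5 (Appendix 2, female stages). The recorded score is S = min(B, P), which is the lesser-stage instruction.

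**Breast advances by one stage, pubic hair fixed.** B can start at 1 to 4 and P can be 1 to 5, giving 4 × 5 = 20 cases. The score goes from min(B, P) to min(B + 1, P). It is unchanged exactly when P ≤ B.

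| Starting B | Values of P that hide the advance | Cases |
|---|---|---|
| 1 | 1 | 1 |
| 2 | 1, 2 | 2 |
| 3 | 1, 2, 3 | 3 |
| 4 | 1, 2, 3, 4 | 4 |
| Total | | 10 of 20 |

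Four of the 10 hidden cases start with equal stages (1/1, 2/2, 3/3, 4/4). The other six start with breast ahead. In the remaining 10 of the 20 cases, breast starts behind pubic hair and the advance is recorded.

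**Pubic hair advances by one stage, breast fixed.** The same count with B and P exchanged gives 10 of 20 hidden.

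**Examples (breast/pubic hair).**
- 2/1 to 3/1: min(2, 1) = 1, then min(3, 1) = 1. No change recorded.
- 2/2 to 3/2: min(2, 2) = 2, then min(3, 2) = 2. No change recorded, although the stages started equal.
- 2/2 to 4/2: min(2, 2) = 2, then min(4, 2) = 2. A two-stage breast advance is not recorded.
- 1/2 to 2/2: min(1, 2) = 1, then min(2, 2) = 2. The advance is recorded.

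**Separate values.** If B and P are both kept, as Section 9.2.14 describes, none of the 20 breast advances and none of the 20 pubic hair advances is lost.

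These are counts of logical combinations. They are not expected proportions of patients.

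**The case against.** The strongest reply is that Appendix 2 may not be the data-capture form. It is marked as reproduced from a journal, the case report form is not among the documents, and an overall score can be read as a summary placed beside two component values. This stands as a limit: it is not shown that the component stages were never collected. It does not remove the contradiction. Section 9.2.14 sends assessors to Appendix 2, and Appendix 2 tells them to choose one stage.

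A second reply is that little depends on the endpoint. That also stands. The Tanner data are summarised without a hypothesis test. Pubertal signals have other routes into the data: menstruation details are recorded at Visit 3 and Visit 10, signs of precocious puberty themselves prompt staging, and physical examination changes that indicate an adverse event are reported as such.

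Several stronger readings are tempting, and the documents do not support them:

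- **That the rule conceals breast development in particular.** The loss is symmetric between the two characteristics.
- **That every girl with differing baseline stages is affected.** An advance must occur first. Advances with breast behind pubic hair are recorded, and some hidden advances start from equal stages, so baseline discordance is the wrong denominator. The documents give no discordance rate in any case.
- **That the hidden change carries into the IGF-1 plot.** SAP Figure 14.1.1 groups patients by baseline stage only. The grouping of girls with differing stages may shift, but no Tanner change is plotted.
- **That the SAP already requires tables of change for each characteristic.** Its sentence about separate values describes the examination; its analysis sentence leaves the tabulated value open.

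**Conclusion.** The point holds as a contradiction between Appendix 2 and both Protocol Section 9.2.14 and SAP Section 5.6.4.6, with a definite direction of bias. Where the Appendix 2 score is what is analysed, the count of girls with a Tanner change cannot exceed the count with an advance in at least one characteristic, and it falls short whenever only the leading characteristic, or one of two equal ones, moves. For boys the problem is an undefined score rather than a biased one.

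The size in patients is unknown. It depends on how often one characteristic advances alone between the two stagings, for which the documents give nothing, and on whether the case report form holds one field or two. The effect is confined to a descriptive secondary endpoint. The correction is worth making because it is simple and the protocol body already describes the better measurement.

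**What to change.** Reconcile Protocol Section 9.2.14, both sheets of Appendix 2 and SAP Section 5.6.4.6:

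1. In Appendix 2, provide separate boxes for breast stage (girls) or genital stage (boys) and for pubic hair stage, and delete the lesser-stage instruction.
2. In Section 9.2.14, say whether the sentence that ends repeat examinations at stage V refers to one characteristic or to both.
3. In SAP Section 5.6.4.6, state that stage and change from baseline are tabulated by arm for each characteristic, and name the characteristic used in Figure 14.1.1.
4. If the case report form already holds both stages, use those values. Where only the overall score was collected, label it for girls as the lesser of the two stages and state that it can hide an advance in a single characteristic.

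The cost is form wording, a few sentences in the SAP and some extra table rows; the same examination yields both stages. New form wording cannot restore component stages that were never written down. The SAP reports blinded data review meetings in March 2019, so for the blinded phase item 4 may be the only remedy left.

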# Tanner Stage 1 (Prepubertal, typically 10 years and younger)

- No glandular tissue; areola follows the skin contours of the chest.
- No pubic hair at all.

#### Tanner Stage 2 (10–11.5 years)

 Breast bud forms, with small area of surrounding glandular tissue; areola begins to widen.† • Small amount of long, downy hair with slight pigmentation on the labia majora.

# Tanner Stage 3 (11.5–13 years)

- Breast begins to become more elevated, and extends beyond the borders of the areola, which continues to widen but remains in contour with surrounding breast.
- Hair becomes more coarse and curly and begins to extend laterally.

#### Tanner Stage 4 (13–15 years)

- Increased breast size and elevation; areola and papilla form a secondary mound projecting from the contour of the surrounding breast.
- Adult-like hair quality, extending across pubis but sparing medial thighs.

# Tanner Stage 5 (15+ years)

- Breast reaches final adult size; areola returns to contour of the surrounding breast, with a projecting central papilla.
- Hair extends to medial surface of the thighs.

The following is to be completed for all male adolescent patients (i.e., 12 to less than 18 years of age at the time of signing the informed consent/assent form).

# Male Genital Development & Pubic Hair

Please check the box next to the most appropriate stage.

#### Tanner Stage 1 (Prepubertal, typically 9 years and younger)

- Testicular volume less than 1.5 mL; small penis of 3 cm or less.
- No pubic hair at all.

#### Tanner Stage 2 (9–11 years)

- Testicular volume between 1.6 and 6 mL; skin on scrotum thins, reddens and enlarges; penis length unchanged.
- Small amount of long, downy hair with slight pigmentation at the base of the penis and scrotum.

# Tanner Stage 3 (11–12.5 years)

- Testicular volume between 6 and 12 mL; scrotum enlarges further; penis begins to lengthen to about 6 cm.
- Hair becomes more coarse and curly and begins to extend laterally.

#### Tanner Stage 4 (12.5–14 years)

- Testicular volume between 12 and 20 mL; scrotum enlarges further and darkens; penis increases in length to 10 cm and circumference.
- Adult-like hair quality, extending across pubis but sparing medial thighs.

#### Tanner Stage 5 (14+ years)

- Testicular volume greater than 20 mL; adult scrotum and penis of 15 cm in length.
- Hair extends to medial surface of the thighs.

# APPENDIX 4 IVRS CALLS FOLLOWING END OF TREATMENT/WITHDRAWAL

Timings of IVRS calls to be made by the patient/caregiver following the date of End of Treatment/Withdrawal in the blinded or OLE phase are summarized overleaf.

#### SPONSOR: GW RESEARCH LIMITED

Study Code: GWEP1521 EudraCT Number: 2015-002154-12 Protocol V8 23Apr19

	Blinded P	'hase a	OLE PI	iase
Relative Day			IMP Not Tapered	IMP Tapered
Date of End of	X	Х		Х
Treatment/Withdrawalb				
+1		Х		
+2		X		
+3		X		
+4		X		
+5		Х		
+6		Х		
+7		Х		Х
+8		Х		
+9		Х		
+10				
+11				
+12				
+13				
+14				
+15				
+16				
+17				
+18				
+19				
+20				
+21				
+22				
+23				
+24				
+25				
+26				
+27	Х		Х	
+28				
+29				
+30				
+31				
+32				
+33				
+34				
+35				
+36				
+37		Х		Х
+38				
+39				
+40				

Note: Gray shading denotes visit windows.

a Only for patients who do not enter the OLE on the day of Visit 10 or for those who withdraw early from the blinded phase.

b Date of End of Treatment/Withdrawal should match the date reported in interactive web/voice response system.

5.7.4	Study Medication Use and Behavior Survey	54
5.7.5	Supplemental Drug Accountability Form	54
5.7.6	Supplemental Adverse Event Form	54
5.7.7	Site Classification Form	55
5.7.8	IVRS Compliance	55
5.8	Changes in the Conduct of the Trial or Planned Analysis	56
6.	REFERENCES	56
7.	AMENDMENTS	56
8.	ATTACHMENTS AND APPENDICES	57

ABBREVIATION

7-COOH-CBD	7-carboxy-CBD	
7-OH-CBD	-	7-hydroxy-CBD
ABCL	-	Adult Behavior Checklist
AEDs	-	Antiepileptic Drugs
AEs	-	Adverse Events
ANCOVA	-	Analysis of Covariance
ALQ	-	Above Limit of Quantification
ATC	-	Anatomical Therapeutic Chemical
BDRM	-	Blinded Data Review Meeting
BLQ	-	Below Limit of Quantification
CBCL	-	Child Behavior Checklist
CBD	-	Cannabidiol
CGIC	-	Caregiver Global Impression of Change
CGICSD	-	Caregiver Global Impression of Change in Seizure Duration
CI	-	Confidence Interval
CMH	-	Cochran–Mantel–Haenszel
CRF	-	Case Report Form
C-SSRS	-	Columbia–Suicide Severity Rating Scale
CWS	-	Cannabis Withdrawal Scale
ECG	-	Electrocardiogram
IGF-1	-	Insulin-like Growth Factor-1
IMP	-	Investigational Medicinal Product
ITT	-	Intention to Treat
IVRS	-	Interactive Voice Response System
LGS	-	Lennox–Gastaut Syndrome
LOCF	-	Last Observation Carried Forward
MAR	-	Missing at Random
MedDRA	-	Medical Dictionary for Regulatory Activities
MI	-	Multiple Imputation
MNAR	-	Missing Not at Random
NOCB	-	Next Observation Carried Backward
NRS	-	Numerical Rating Scale
OLE	-	Open Label Extension
PCWS	-	Pediatric Cannabinoid Withdrawal Scale

PGIC	-	Physician Global Impression of Change
PK	-	Pharmacokinetics
PP	-	Per Protocol
QOLCE	-	Quality of Life in Childhood Epilepsy
QOLIE-31-P	-	Quality of Life in Epilepsy, version 2
RM	-	Rescue Medication
SAP	-	Statistical Analysis Plan
SGIC	-	Subject Global Impression of Change
SGICSD	-	Subject Global Impression of Change in Seizure Duration
SOC	-	System Organ Class
SCQ	-	Social Communication Questionnaire
TAND	-	TSC-associated Neuropsychiatric Disorders
TEAE	-	Treatment Emergent Adverse Event
TSC	-	Tuberous Sclerosis Complex
ULN	-	Upper Limit of Normal
Vineland-II	-	Vineland Adaptive Behavior Scales, Second Edition

1. INTRODUCTION

This statistical analysis plan (SAP) documents the statistical reporting to be performed for trial GWEP1521.

This SAP has been prepared based on the following protocol:

- Protocol GWEP1521 (Version 8, dated 23rd April 2019).

1.1 Rationale

Tuberous sclerosis complex (TSC) is a genetic disorder characterized by the formation of nonmalignant tumors (tubers) in multiple organ systems. The clinical signs of TSC arise as a result of inactivating mutations in either of two tumor suppressor genes: *TSC1* (located on chromosome 9q34.13) or *TSC2* (located on chromosome 16p13.3). Thus, inactivating mutations in *TSC1* and *TSC2* lead to inadequate suppression of mTOR signaling, resulting in abnormal cellular growth and tumorigenesis.

Mutations in *TSC1* account for approximately 15% of all cases of TSC whilst approximately 70% of all cases are due to mutations in *TSC2*; ~15% of TSC patients have no identifiable mutation in the coding regions of either gene. Generally, *TSC2* mutations result in a more severe disease phenotype compared with *TSC1* mutations. The birth incidence of TSC is estimated to be 1 in 6,000 with approximately 50,000 individuals in the United States and 1 million individuals worldwide affected.

Tumors in TSC patients can occur in any major organ yet develop primarily in the brain, eyes, heart, kidney, skin and lungs.

Epileptic seizures are the most common clinical manifestation of TSC, affecting more than 70% of patients. Seizure onset occurs within the first year of life in approximately two-thirds of TSC patients and occurs within the first 3 years of life in 80% of TSC patients. The onset of epilepsy in TSC commonly manifests as focal motor seizures, which in approximately one-third of TSC patients coexist with infantile spasms.

Virtually all TSC patients with infantile spasms and approximately half of all epileptic TSC patients without them develop multiple seizure types, including complex focal seizures (with or without secondary generalization), generalized tonic–clonic seizures, atonic seizures, and atypical absences. Although infantile spasms resolve with time, the frequency and severity of other seizures tend to increase throughout early childhood and nearly two-thirds of TSC patients develop medically intractable epilepsy, including Lennox–Gastaut syndrome.

Early management of seizures is therefore important in preventing subsequent epileptic encephalopathy and in reducing the associated cognitive and neuropsychiatric consequences.

The pharmacological therapies currently available for TSC-associated epilepsy often produce serious adverse effects, and a significant proportion of patients (37–63%) become resistant to treatment. Consequently, there is a clear need for new, efficacious pharmaceutical treatments for refractory epilepsy. Given the limitations of current synthetic antiepileptic drugs (AEDs), it has been suggested that CBD should be tested for anticonvulsive efficacy in randomized controlled clinical trials, especially in infantile epileptic syndromes. Although there are no published reports to date investigating the efficacy of CBD for seizures in TSC patients, a recent parent survey has reported that 84% of children with treatment-resistant epilepsy experienced a reduction in seizures whilst taking CBD-enriched cannabis, with over half of those reporting >80% reduction in seizure frequency.

The CBD-enriched cannabis was behaviorally well tolerated and children often experienced improved sleep, increased alertness, and better mood.

